9.5.1.3 Classifications for adverse event assessment

All AEs will be assessed and documented by the investigator according to the categories detailed below.

Seriousness

For each AE, the seriousness must be determined according to the criteria given in Section 9.5.1.1.

Intensity

The intensity of an AE should be documented using the NCI-CTCAE v4.03. For events not listed in the NCI-CTCAE, the following scale will be used:

- Grade 1: Mild
- Grade 2: Moderate
- Grade 3: Severe
- Grade 4: Life-threatening □ Grade 5: Fatal

Causal relationship

The assessment of the causal relationship between an AE and the administration of treatment is a decision to be made by the investigator, who is a qualified physician, based on all information available at the time of the completion of the CRF.

The assessment is based on the question whether there was a “reasonable causal relationship” to the study treatment in question.

Possible answers are “yes” or “no”

An assessment of “no” would include:

1. The existence of a highly likely alternative explanation, e.g. mechanical bleeding at surgical site.

or

2. Non-plausibility, e.g. the patient is struck by an automobile when there is no indication that the drug caused disorientation that may have caused the event; cancer developing a few days after the first drug administration.

An assessment of “yes” indicates that that the AE is reasonably associated with the use of the study treatment.

Important factors to be considered in assessing the relationship of the AE to study treatment include:

- The temporal sequence from drug administration: The event should occur after the drug is given. The length of time from drug exposure to event should be evaluated in the clinical context of the event.
- Recovery on drug discontinuation (de-challenge), recurrence on drug re-introduction (re-challenge): Patient’s response after de-challenge or re-challenge should be considered in view of the usual clinical course of the event in question.
- Underlying, concomitant, intercurrent diseases:
Each event should be evaluated in the context of the natural history and course of the disease being treated and any other disease the patient may have.
- Concomitant medication or treatment:
The other drugs the patient is taking or the treatment the patient receives should be examined to determine whether any of them might have caused the event in question.
- Known response pattern for this class of drug: Clinical/preclinical.
- Exposure to physical and/or mental stresses: The exposure to stress might induce adverse changes in the recipient and provide a logical and better explanation for the event.
- The pharmacology and pharmacokinetics of the study treatment:
The pharmacokinetic properties (absorption, distribution, metabolism and excretion) of the study treatment, coupled with the individual patient’s pharmacodynamics should be considered.
- The assessment is not possible.

Causal relationship to protocol-required procedure(s)

The assessment of a possible causal relationship between the AE and protocol-required procedure(s) is based on the question whether there was a “reasonable causal relationship” to protocol-required procedure(s).

Possible answers are “yes” or “no”.

Action taken with study treatment

Any action on study treatment to resolve the AE is to be documented using the categories listed below.

- Drug withdrawn
- Drug interrupted
- Dose reduced
- Dose not changed
- Not applicable
- Unknown

Other specific treatment(s) of adverse events

- None
- Remedial drug therapy
- Other

Outcome

The outcome of the AE is to be documented as follows:

- Recovered/resolved
- Recovering/resolving
- Recovered/resolved with sequelae
- Not recovered/not resolved
- Fatal
- Unknown

9.5.1.4 Assessments and documentation of adverse events

AEs observed, mentioned upon open questioning by a member of the investigator team or spontaneously reported by the patient will be documented in the patient's records and on the appropriate CRF. AEs will be documented in an event-based manner, using NCI-CTCAE version 4.03 guidelines. In addition, since the NCI-CTCAE may not adequately capture the severity of new corneal epitheliopathy, an alternative severity grading system for ocular adverse drug reactions will be used (see **Table 2-6** and **Table 2-7**).

9.5.1.5 Reporting of serious adverse events

The definition of SAEs is given in Section 9.5.1.1. Each SAE must be followed up until resolution or stabilization by submission of updated reports to the designated recipient.

It is not mandatory to report new SAEs occurring after the protocol-defined observation period, however, at the investigator's discretion these may be reported if considered potentially relevant. In such cases, the SAEs will be processed by the sponsor according to all applicable regulations.

Investigator's notification of the sponsor

The Investigator/ Sponsor shall report to Bayer within 24 hours of the investigator's awareness of other events such as:

An adverse event related to study specific procedures.

Any new and important event related to treatment with the study drug(s).

Any pregnancy during which a female patient was exposed to the study drug(s).

Any pregnancy in the partner of a male patient, where the male patient was exposed to study drug at the time of conception or conception occurred within two weeks of the last dose of study drug(s).

Any other relevant safety information including but not limited to reports on drug interaction, overdose, drug abuse or misuse, drug dependency, withdrawal syndrome, medication error, occupational exposure and lack of drug effect (LODE) occurring at any time during the treatment phase;

Any communication concerning safety related information to regulatory authorities or ethics committees including but not limited to:

- Development Safety Update Reports (DSUR) / relevant parts of IND reports for the STUDY;
- Any other safety related reports, issues and queries that are either raised by or communicated to regulatory authorities or ethics committees;

The Investigator/Sponsor may report SAEs using: A

MedWatch form available at <http://www.fda.gov/medwatch/>

All reports shall be sent electronically to:

Electronic Mailbox: [contact]

[contact]

Address: Global Pharmacovigilance - USA

Mail only Bayer HealthCare

[name]

[name]

Address: [name]

FDX or UPS only [name] for UPS

Reports for all Bayer products can also be phoned in via our Medical Communications Department

[contact]

All investigators will be thoroughly instructed and trained on all relevant aspects of the investigator's reporting obligations for SAEs. This information, including all relevant contact details, is summarized in the investigator site file. This information will be updated as needed.

The investigator must report immediately (within 24 hours of the investigator's awareness) all SAEs occurring during the observation period defined in Section 9.5.1.3 to the Yale Center for Clinical Investigation (YCCI) Project Manager as detailed in the instructions for SAE reporting included in the Investigator File. For this, an AE page in the CRF as well as the complementary pages provided in the Investigator File must be completed for each SAE.

SAEs occurring after the protocol-defined observation period will be processed by the sponsor according to all applicable regulations.

If disease progression leads to signs and symptoms that meet the criteria for seriousness (see Section 9.5.1.1), the associated signs and symptoms should be reported as SAE, not the underlying cause (i.e. "progressive disease" should not be recorded as SAE). **In this case, disease progression should be mentioned on the SAE form as "alternative explanation"**. If a new primary malignancy is noted at any time before end of active follow-up, it must be reported as an SAE, whether or not it is assessed as related to study treatment.

For documentation of laboratory findings as SAE, please refer to Section 9.5.3.1.

Notification of the IECs / IRBs

Notification of the IECs / IRBs and Bayer Health Care about all relevant events (e.g. SAEs, suspected, unexpected, serious adverse reactions [SUSARs]) will be performed by the sponsor and/or by the investigator according to all applicable regulations and local policies.

All SAEs, whether originating at Yale or at collaborating sites, meeting the criteria for prompt reporting will be reported to the Yale University Human Investigation Committee (HIC) as per IRB Policy 710.

The Yale University HIC prompt reporting criteria are: Unexpected (in terms of nature, specificity, severity, or frequency) AND related or possibly related to participation in the research AND the research places subjects or others at greater risk of harm (including physical, psychological, economic, legal, or social harm) than was previously known or recognized. Collaborating sites should report adverse events to their local IRB per institutional policy.

Notification of the authorities

The processing and reporting of all relevant events (e.g. SAEs, SUSARs) to the authorities will be done by the sponsor according to all applicable regulations.

Sponsor's notification of the investigational site

The sponsor will inform all investigational sites about reported relevant events (e.g. SUSARs) according to all applicable regulations.

9.5.1.5 Expected adverse events

For this study, the applicable reference document for anetumab ravtansine is the most current version of the IB.

Overview listings of frequent events that have occurred so far in the clinical development are shown in the current IB. If relevant new safety information is identified, the information will be integrated into an update of the IB and distributed to all participating sites.

The expectedness of AEs will be determined by the sponsor according to the applicable reference document and according to all local regulations.

9.5.1.6 Adverse events of special safety interest

Anetumab ravtansine is an investigational drug and current knowledge of the AEs associated with this compound is limited.

As with any new chemical entity, there is always potential for unexpected AEs, including hypersensitivity reactions.

Corneal disorders are considered as AEs of special interest. Specific dose modification schemes are defined in Section 7.3.2.1. An alternative severity grading system for ocular adverse drug reactions will be used in addition to NCI-CTCAE version 4.03 criteria, since the NCI-CTCAE may not adequately capture the severity of these novel adverse reactions (see **Table 2-6** and **Table 2-7**).

There is no need to report corneal toxicities as SAEs unless they meet the criteria for an SAE as defined in Section 9.5.1.1; however these events will need to be closely monitored and reviewed, and documented timely and accurately both in source data and on the CRF. Details of ophthalmologic examination will be documented on the "ophthalmologic examination" CRF page and in case AEs occur, also on "AE" CRF page, ensuring the reporting terminology used on those pages matches and reflects the source.

9.5.2 Pregnancies

The investigator must report to the sponsor any pregnancy occurring in a female study patient during her participation in this study. The outcome of the pregnancy should be followed up carefully, and any outcome of the mother and the child at delivery should be reported.

The child's health should be followed up until 4 weeks after birth.

For a pregnancy in the partner of a male study patient, all efforts will be made to obtain similar information on course and outcome, subject to the partner's consent.

For all reports, the forms provided are to be used. The investigator should submit them within the same timelines as an SAE.

9.5.3 Further safety

9.5.3.1 Laboratory evaluations

Safety laboratory analyses will be performed locally according to the schedule summarized in the flow chart of Section 9.1.

Complete blood count: Hemoglobin, hematocrit, platelet count, white blood cell count (WBC). WBC must include differential including neutrophil, lymphocyte, monocyte, basophil, and eosinophil counts.

Electrolyte and chemistry panel: sodium, potassium, chloride, bicarbonate, calcium, phosphorus, glucose (fasting or random/unspecified), AST, ALT, gamma-glutamyl transferase (GGT), bilirubin (total and direct), ALP, uric acid, total protein, albumin, lipase, amylase, lactic dehydrogenase (LDH), blood urea nitrogen (BUN) or urea, and creatinine.

Coagulation panel: PTT, and PT or PT-INR.

Urinalysis: Only dipstick test will be done, and complete urinalysis (e.g. microscopic analysis of the urine sediment) will only be done if the dipstick results are indicative or clinically indicated.

Serum pregnancy test in WOCBP. Test should be repeated at least every 6 weeks until safety follow-up visit. Postmenopausal women who have not had periods for more than 1 year without an alternative medical cause or surgically sterilized women will not be required to undergo a serum pregnancy test (this information should be recorded under medical history on the CRF).

eGFR according to the MDRD abbreviated formula (see Appendix 16.6).

An isolated laboratory abnormality that meets the criteria for a CTCAE Grade 4 classification is not reportable as an SAE, unless the investigator assesses that the event meets standard International Conference on Harmonization (ICH) criteria for an SAE (see SAE definition in Section 9.5.1.1). All laboratory abnormalities, including CTCAE Grade 4 abnormalities, will be documented on the laboratory CRF.

9.5.3.2 Physical examination

Physical examinations will be performed according to the schedule summarized in the flow chart of Section 9.1. Clinically significant abnormal physical examination findings are recorded either as medical history or as AEs (see Section 9.5.1.1).

Complete physical examination

Complete physical examination of all organ systems per usual standards.

Brief physical examination

Brief physical examination includes, but is not limited to, review of organ systems and physical areas of symptomatic concern or investigator's degree of suspicion for any abnormality. After Cycle 1, brief physical examinations are only mandatory on Day 1 of each cycle and are optional as per local practice at Day 8 and Day 15 visits.

9.5.3.3 ECOG Performance Status

Change of ECOG PS will be measured for safety reason; grading definitions are given in Appendix 16.1. ECOG PS will be assessed at prescreening, full screening, on Day 1 of each cycle and at safety follow-up visit (see flow chart in Section 9.1).

9.5.3.4 Vital signs

Body weight, height, heart rate, blood pressure, body temperature, and respiratory rate will be assessed according to the schedule summarized in the flow chart of Section 9.1. Any clinically relevant measurements or changes are to be reported as AEs (e.g. weight gain or loss, hypertension, tachycardia, bradycardia, etc.).

9.5.3.5 12-lead ECG

12-lead ECGs will be performed according to the schedule summarized in the flow chart of Section 9.1. The overall interpretation of the ECG (normal/abnormal, clinical relevance) and the ECG diagnosis will be documented in the source documents and on the CRF. This review should be completed by a qualified physician and signed and dated at the time of review.

9.5.3.6 Cardiac function

Cardiac function test is mandatory. It will be measured by EchoCG or MUGA scan at full screening and on C2D1, C4D1, and afterwards at the investigator's discretion based on clinical need (see flow chart in Section 9.1). EchoCG shall be performed instead of MUGA when local regulations do not permit the use of MUGA as requested per protocol schedule.

9.5.3.7 Ophthalmologic examinations

Corneal toxicity has been identified as a TEAE of special interest for which a causal relationship with anetumab ravtansine has been deemed probable by the investigators in Phase I trial. A detailed ophthalmologic examination (visual acuity [BCVA according to ETDRS, or Snellen, or Landolt C or other charts], IOP, dry eye test [Schirmer test] and slit lamp) will be done for all patients during full screening within 3 weeks before the start of study treatment (see flow chart in Section 9.1). Visual acuity test and slit lamp examination will be repeated before infusion in every cycle except C1D1, and at safety follow-up visit, or more frequently at investigator's discretion (**important to refer to Table 2-6 and Table 2-7**).

IOP measurement is to be repeated during anetumab ravtansine therapy if the patient receives steroid eye drops as treatment for eye toxicity. IOP measurements should be repeated at two weeks and six weeks after starting topical corticosteroids for any subjects who are treated with topical corticosteroids for more than ten days. If neither the two week nor the six week IOP evaluation reveal elevated IOP (i.e., IOP increase by ≥ 7 mmHg), the frequency of IOP

evaluations can be reduced to every 4 months. If IOP evaluation reveals an elevated IOP, appropriate medical management should be initiated with follow-up appropriate for the elevation in IOP. Changes in IOP should be managed by the investigator. The remedial therapy should be chosen at investigator's discretion or according to the institutional standards; therapeutic measures can include modification of the type or posology of topical steroid eye drop, initiation of topical IOP lowering drugs and any other therapeutic options according to the local SoC. Ophthalmological monitoring should be maintained until the IOP has returned to normal values.

Dry eye (Schirmer) tests will be repeated at C1D1 (if screening period Schirmer test is conducted within 7 days of starting study treatment, the test does not need to be repeated at C1D1), and on treatment prior to C4D1 and C7D1. Schirmer tests may be repeated more frequently during treatment at investigator's discretion (e.g. in case of eye dryness during anetumab ravtansine therapy).

During treatment, ophthalmologic examination can be done up to 7 days before anetumab ravtansine infusion.

9.6 Other procedures and variables

9.6.1 Biomarkers

Preclinical and Phase I evidence suggests that mesothelin expression (or expression level above a certain threshold) in human tumors may be required for binding, internalization, and anti-tumor activity of anetumab ravtansine. All patients will have formalin-fixed, paraffin-embedded (FFPE) tumor samples available for IHC determination of mesothelin expression at prescreening as a potential predictive biomarker (see also flow chart in Section 9.1). In the absence of archival tissue, fresh biopsies may be used if deemed safe by the investigator and there is no additional risk for the patient in the investigator's judgement. Only patients whose tumors express mesothelin at staining intensity of moderate (2+) or stronger (3+) in at least 30% of tumor cells will participate further in this study. Mesothelin levels will be determined using an IHC assay (clone SP74).

In addition to obligatory measurement of mesothelin expression levels, biomarker plasma (from whole blood) will be collected on C1D1 pre-dose, C6D1 (+/- 1 cycle), and at end of treatment if possible, to be banked for future correlative research.

Exploratory biomarker analysis may also be performed using additional tumor tissue for future studies of scientific interest; these might include alterations in tumor-associated genes and to perform gene expression analysis.

The exploratory biomarkers may include, but are not limited to, DNA sequencing of tumor-associated genes and gene expression profiling. Next generation sequencing (NGS), and RNA, protein or miRNA expression analysis may be performed.

In addition to the biomarkers listed above, other biomarkers deemed relevant to gain further knowledge about the pathomechanism of the disease or about the drug (i.e. mode of action-

related effect or safety of the drug) and/or the pathomechanism of the disease may be measured, based on newly emerging data from other ongoing studies and/or literature data.

Details on the collection, processing, storage and shipment of biomarker samples will be provided in separate documents (e.g. sample handling sheets or lab manual).

9.7 Appropriateness of procedures / measurements

The efficacy assessments used in the study include those considered SoC to evaluate antitumor activity in patients with advanced or metastatic pancreatic cancer.

The safety assessments are appropriate and standard to monitor safety and assess toxicity.

Appropriateness of RECIST criteria. RECIST 1.1 criteria, designed to assess response of solid tumors is highly appropriate for determination of the primary endpoint of RR.

10. Statistical methods and determination of sample size

10.1 General considerations

Statistical analysis will be performed using SAS version 9.2 or later; the version used will be specified in the SAP.

In general, continuous variables will be summarized using number of non-missing values (n), number of missing values, means, standard deviations, medians, maximum, minimum, and interquartile range.

Ordinal variables will be summarized using n, number of missing values, medians, maximum, minimum, and interquartile range.

Categorical variables will be summarized using n, number of missing values, and percentages.

Time-to-event variables will be summarized using Kaplan-Meier estimates.

Further details on the statistical analyses will be provided in the SAP.

10.2 Variables and planned statistical analyses

10.2.1 Population characteristics

Population characteristics (see Section 9.3) will be reported by summary statistics and listings. Further details will be described in the SAP.

10.2.2 Primary efficacy variable

Response rate is defined as time from start of treatment until disease progression (according to RECIST, per blinded radiology review) or death. Patients not experiencing death or progression will be censored at the last tumor assessment.

Additional details, including additional censoring rules, will be described in the SAP.

10.2.2.1 Primary efficacy analysis

The primary efficacy analysis tests the following hypotheses:

H0: In patients with advanced or metastatic pancreatic cancer overexpressing mesothelin and pretreated with prior chemotherapy, a response per RECIST under treatment with anetumab ravtansine at 6.5 mg/kg Q3W would not be seen.

versus

HA: In patients with advanced or metastatic pancreatic cancer overexpressing mesothelin and pretreated with prior chemotherapy, a response per RECIST under treatment with anetumab ravtansine at 6.5 mg/kg Q3W would be seen.

The minimax, Simon 2-stage design testing 5% null hypothesis versus a 21% alternative requires a maximum of 30 patients. If there are no patients exhibiting any response among the first 20 then the trial will terminate early. If there is at least one response among the first 20 then the trial will accrue an additional 10 patients for a maximum of 30. Four or more responses out of 30 will reject the null hypothesis in favor of the 21% response alternative. These criteria have significance level (alpha) 0.1 and power 90%. The probability of stopping early is 36% if the response rate is 5% or lower. The expected sample size is 26.4.

Sensitivity analyses will be performed, including analyses to assess the impact of missing data and the possibility of survivorship and selection biases. Further details will be described in the SAP.

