3.2 Rationale of the study

The need for new treatments for pancreatic cancer is great. At the MTD of 6.5 mg/kg Q3W, anetumab ravtansine has demonstrated a tolerable safety profile and efficacy in pancreatic cancer. If this study shows promise, with at least 21% of treated patients showing RECIST response, or prolonged delay in progression compared with historical controls, this would suggest the potential to impart large clinical benefit and warrant larger controlled trials.

4. Study objectives

The primary objective of this study is to:

- Test the activity/response rate per RECIST 1.1 criteria of anetumab ravtansine in patients with advanced pancreatic cancer who stain for mesothelin expression

The secondary objectives of this study are to:

- Time to Progression (TTP) defined as time from study treatment to RECIST 1.1 progression, or death (others going off study will be censored)
- Toxicity in pancreatic cancer patients (at 6.5 mg/kg dose)

5. Study design

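### Do the worded hypotheses in section 10.2.2.1, which turn on whether a response is seen, conflict with the 5% versus 21% test?

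*Combined protocol and SAP*

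**What the plan says.** Section 10.2.2.1 opens with "The primary efficacy analysis tests the following hypotheses" and gives a pair of sentences. For pretreated, mesothelin-overexpressing advanced or metastatic pancreatic cancer, H0 is that "a response per RECIST under treatment with anetumab ravtansine at 6.5 mg/kg Q3W would not be seen". HA is that "a response per RECIST under treatment with anetumab ravtansine at 6.5 mg/kg Q3W would be seen". Neither sentence contains a response rate.

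The paragraph directly below gives the design:

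- Rates and size: "The minimax, Simon 2-stage design testing 5% null hypothesis versus a 21% alternative requires a maximum of 30 patients".
- Stage 1: the trial stops if none of the first 20 patients responds. Otherwise, "If there is at least one response among the first 20 then the trial will accrue an additional 10 patients".
- Final rule: "Four or more responses out of 30 will reject the null hypothesis in favor of the 21% response alternative".
- Stated properties: significance level 0.1, power 90% and expected sample size 26.4. On early stopping: "The probability of stopping early is 36% if the response rate is 5% or lower".

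The same rates, stage 1 rule and cutoff appear in the synopsis (study design and plan for statistical analysis) and in section 5.1.

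Section 3.2, the rationale, describes a promising result as one "with at least 21% of treated patients showing RECIST response, or prolonged delay in progression compared with historical controls".

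**The concern.** The hypothesis sentences announce what the primary analysis tests, and taken literally they describe a null response rate of zero. One confirmed responder would settle that. The design underneath has another null, 5%. It treats one responder in the first 20 as a reason to continue, and it needs four in 30 before it rejects.

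The printed operating characteristics cannot belong to a zero-rate null. At a true rate of zero the trial would always stop after stage 1, the expected sample size would be 20 and the type I error would be 0.

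If the literal reading governed, a trial with one, two or three responses would fail to reject a null that its own data contradict. A report could then cite the protocol's HA as met in a trial that missed its criterion. Section 3.2 seems to add a further benchmark: 21% of 30 is 6.3, so at least 7 responders (6/30 = 20.0%, 7/30 = 23.3%), or delayed progression against historical controls that are not specified.

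**Working it through.** **Inputs**, all from section 10.2.2.1: n1 = 20, stop at 0 responses; 10 further patients, n = 30; reject at 4 or more; p0 = 0.05; p1 = 0.21.

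**Formulas** (exact binomial):

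- Early stopping: S(p) = (1 − p)^20.
- Expected sample size: 20 + 10 × (1 − S).
- Rejection: R(p) = P(Bin(30, p) ≥ 4) − S(p) × P(Bin(10, p) ≥ 4). The second term removes trials that stopped at stage 1 but would have reached four had they continued.
- Passing stage 1 and ending with 1 to 3 responses: 1 − S − R.

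**Step 1: reproduce the plan's figures.**

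- S(0.05) = 0.95^20 = 0.3585 (plan: 36%). At rates below 5% it is larger, for example 0.5438 at 3%, so 36% is the minimum over the null range.
- Expected sample size at 5% = 20 + 10 × 0.6415 = 26.4 (plan: 26.4).
- R(0.05) = 0.0608 − 0.3585 × 0.0010 = 0.0604. The plan's 0.1 is the limit used to choose the design, and the attained level lies below it.
- R(0.21) = 0.9016 − 0.0090 × 0.1391 = 0.9003 (plan: 90%).

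A search over two-stage designs with type I error at most 0.10 and power at least 0.90 returns the same minimax design: stop at 0 of 20, reject at 4 or more of 30.

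**Step 2: the literal null, p = 0.** S = 1, expected sample size = 20, R = 0. The printed 36% and 26.4 do not fit this null. The printed figures therefore show which null the design tests, and it is 5%.

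**Step 3: where sentence and rule part company.** With no response in 20, neither supports activity. With four or more in 30, both do. They differ only for 1 to 3 responses:

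| True rate | Stop at stage 1 | 1–3 responses | Rule rejects |
|---|---|---|---|
| 5% | 0.3585 | 0.5811 | 0.0604 |
| 8% | 0.1887 | 0.5966 | 0.2147 |
| 10% | 0.1216 | 0.5274 | 0.3510 |
| 15% | 0.0388 | 0.2848 | 0.6764 |
| 21% | 0.0090 | 0.0907 | 0.9003 |

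**Step 4: what the plan does with 1 to 3 responses.** The final rule gives one answer: the null is not rejected. Nowhere in the document does one response lead to rejection. Section 10.2.2.1 gives one response in the first 20 a different consequence, the accrual of 10 more patients.

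**Step 5: does the wording open a false-positive route?** The null range that the plan uses for early stopping is every rate up to 5%, which includes zero. The chance of rejection under the rule is 0 at p = 0 and 0.0604 at p = 0.05, so the 0.1 limit holds under either reading. Any trial that rejects by the rule also contradicts the worded H0.

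**The case for a change.** The strongest argument for a change is that formal hypotheses should describe the test that is run, and these do not. The disagreement region is not remote. At a true rate of 5% the worded null would be contradicted in 0.64 of trials (1 − 0.3585), while the rule rejects in 0.06. Section 10.2.2, just above, does not help a reader recover the intended quantity, because it defines response rate as a time to progression or death. Nor does section 10.2.2.1 defer the hypotheses to a later SAP; it defers only the detail of the sensitivity analyses. The repair would take one line.

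The first point stands: the sentences are imprecise. The rest does not make that a defect in the plan. The 0.64 and 0.58 compare the plan's rule with a one-response test found nowhere in the document. The synopsis and section 5.1 also show how the authors use the idea of a response being seen: they equate none in 20 with a rate under 5%, and one or more with a rate of at least 5%. That is loose shorthand around the 5% mark, and a zero-rate null is not what they meant. The definition in section 10.2.2 is a separate problem that leaves the null rate and the cutoff untouched. Section 3.2 is background. It sets no test, and time to progression is a secondary objective summarised by Kaplan-Meier with no hypothesis or threshold attached.

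**Conclusion.** This is a clerical slip in two sentences, and no change to the plan follows. The null is stated numerically in the same section, the rejection rule is explicit, and the synopsis and section 5.1 agree with it. An analyst with one, two or three responses in 30 has one documented conclusion to report: the 5% null is not rejected.

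Aligning the wording would leave the sample size (30), stage 1 rule (0 of 20), cutoff (4 of 30), attained type I error (0.0604), power (0.9003) and early-stopping probability (0.3585) exactly as they are. The effect on conduct and on the conclusion is nil. The 0.58 and 0.64 should not be quoted as error rates of this trial.

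The figures assume independent responses with a common response rate and that the first 20 and all 30 patients are counted as the rule states. The conclusion also rests on the numerical rule governing the decision, and nothing in the document suggests otherwise.
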